After the completion of the MRI scan, the coordinator will accompany the study participant to the clinic for TCD recordings. There, the participant will receive a second hypercapnia challenge (using the same conditions described above) while undergoing TCD recording. Pulse wave velocity (PWV) may be measured at this time.

Treatment period:

All participants will treat twice daily, at least one hour apart. Each treatment duration is 19 minutes 39 seconds. Participants will only wear the device when administering a treatment per protocol. The treatment period is anticipated to last for 12 weeks. However, treatment may be

extended for approximately 2 additional weeks in the case of scheduling conflicts (such as those imposed by standard operating procedures imposed by WFU to limit the spread of COVID-19). Patients should continue to treat twice daily up until the time of the end of treatment clinic visit.

Interim phone calls:

- Participants will be called the next day after their Device training visit to confirm that participants were able to successfully administer treatment in the home setting.
- Scheduled follow up phone calls will be made at week 3, week 6 and week 9. During these calls, the coordinator will ask about any adverse events, any changes to concomitant medications and to confirm no issues have arisen with use of the Device.
- Participants will also have received the contact information for the site coordinator so that they may report potential adverse events or issues with the Device in real time.

End of treatment visit (remote) – week 12:

During this remote visit, the study coordinator will administer the NMSS, the MDS-UPDRS parts II and IV as well as the modified MDS-UPDRS part III. They will also administer the MoCA, the MRI safety screening as well as a Device usability questionnaire. Participants will then be asked to completed the (PROs) including the Geriatric Depression Scale (GDS), the Parkinson's Anxiety Scale (PAS), the Epworth Sleepiness Scale (ESS), the Functional Assessment of Chronic Illness Therapy – Fatigue (FACIT-F) and the Device Usability Questionnaire and to bring them to their scheduled imaging visit. Participants will also be told to bring their Devices with them to the next clinic but that they should continue with twice daily treatments until their imaging visit.

End of treatment visit (in clinic)- week 12, 1 day after remote visit:

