Participants will be screened for COVID-19 upon arrival to the clinic. Effort should be made to schedule the imaging visit within 24 hours of the virtual visit. On arrival, the MDS-UPDRS part III and the Timed Up and Go (TUG) will then be administered. The bilateral ear exam will be performed. Participants will then undergo the Magnetic Resonance Imaging (MRI) protocol and the transcranial Doppler sonography recordings of a hypercapnia challenge outlined above. Pulse wave velocity may be measured at the time of the transcranial Doppler sonography recordings. The PROs will be collected and checked for completeness. Participants will be asked to complete missing items or complete in full in the clinic if forms were left at home. Devices will be collected. The Inventory Control Log should be updated noting the return date of the Device. The Device should then be returned to Robling with a completed Device Return Form. **Should participants forget to bring their TNM™ Device to this visit, they will be provided with an addressed pre-paid FedEx box that can be used to ship the Device directly back to Robling. Coordinators should check tracking information and follow up with reminder phone calls to ensure return of the Device.

Follow up visit (remote) – week 17:

During this remote visit, the study coordinator will administer the NMSS, the MDS-UPDRS parts II and IV as well as the modified MDS-UPDRS part III. They will also administer the MoCA, the MRI safety screening. Participants will then be asked to complete the (PROs) including the Geriatric Depression Scale (GDS), the Parkinson's Anxiety Scale (PAS), the Epworth Sleepiness Scale (ESS) and the Functional Assessment of Chronic Illness Therapy – Fatigue (FACIT-F) and to bring them to their scheduled imaging visit.

Follow up visit (in clinic)- week 17, 1 day after remote visit:

Participants will be screened for COVID-19 upon arrival to the clinic. Effort should be made to schedule the imaging visit within 24 hours of the virtual visit. On arrival, the MDS-UPDRS part III and the Timed Up and Go (TUG) will then be administered. Participants will then undergo the Magnetic Resonance Imaging (MRI) protocol. A bilateral ear exam will only be performed if there were residual ear-related AEs at the last treatment visit.

SCHEDULE OF ACTIVITIES

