Activity	Recruitment (if in person)	Screening visit (remote)	Baseline /device training visit week 0 or here	Phone contact (1 day after training)	Phone contact week 3	Phone contact week 6	Post- treatment remote visit	Post- treatment treatment week 12 clinic visit	Follow up visit week 17 (remote)	Follow up visit week 17 clinic visit
Informed Consent	x		x							
Try on unpowered device										
Review study inclusion/exclusion criteria	x									
Medical History and concomitant medications		x								
Watch informational video		x								
Non-Motor Symptom Scale	x	x					x		x	
MDS-UPDRS part I	x	x					x		x	
MDS-UPDRS part II	x	x					x		x	
MDS-UPDRS part III (on-state)	x	x					x		x	
MDS-UPDRS part IV	x	x					x		x	
Timed Up and Go	x						x		x	
Montreal Cognitive Assessment	x						x		x	
Geriatric Depression Scale	x						x		x	
Parkinson's Anxiety Scale	x						x		x	
Epworth Sleepiness Scale	x						x		x	
Functional Assessment of Chronic Illness Therapy - Fatigue	x						x		x	
MRI safety screening	x						x		x	
Temperature check/ COVID-19 screening questions	x						x		x	
Device training	x						x			
Device usability questionnaire										
Check in to confirm first at-home treatment							x			
Ear physical exam	x							x		
Pregnancy test (if appropriate)	x							x		
Review concomitant medications and adverse events	x	x			x	x	x	x	x	x
rs- pCASL	x							x		x
rs-fMRI BOLD	x							x		x
pCASL (hypercapnia challenge)	x							x		x
TCD (hypercapnia challenge)	x							x		x
Device collection										
Pulse wave velocity	x									

Selection Criteria

Inclusion Criteria:

Each participant must have a pre-treatment history that, when initially screened by a principal investigator or designee, documents that she/he meets all elements of the following:

- Must be 21-85 years old.
- Diagnosed with Parkinson's Disease (meeting UK PD Society Brain Bank criteria)
- Responsive to oral DRT (dopamine replacement therapy) and treated with oral DRTs for a minimum of 3 years prior to screening visit
- Participants and investigators must expect that the participant will be able to remain on a stable regimen of concomitant therapies used for the management of PD motor and non-motor symptoms and not to introduce new medications used to treat motor or non-motor symptoms associated with PD during the clinical trial. See details in the **Concomitant Medication** Section.
- Must be able to voluntarily give written informed consent.
- Must be willing and able to comply with study requirements

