Packets containing 4 sealed envelopes with the printed bar codes for randomization assignments will be provided by the Device sponsor. Each batch will contain two stimulation 1 and two stimulation 2 assignments. The envelopes will be randomly shuffled by an agent not involved with the study. A given packet will be completed before the next packet is opened. The device-training coordinator will load the treatment onto the device, will record the device number allocated to the participant and will train the participant according to the training script provided (see Study Coordinator Quick Reference Guide). If the participant makes a comment about feeling warming or cooling sensations that may potentially unblind the study staff to treatment allocation, this information is not to be shared with other study staff including other coordinators, the principal investigator, Device sponsor CRA, data analysts or the study statistician. All assessments will be performed by a study coordinator that does not take part in the interim phone calls. Participants will be told that pain should not be associated with treatment, and if they do experience pain, that they should stop treatment and contact the coordinator immediately and/or seek medical attention if necessary. However, they will also be told that in the absence of pain, for the integrity of the trial, they should not discuss their treatment experience with anyone associated with the study (e.g. other research staff, their caregiver or other people they may know are participating in the trial). The exception being when they are specifically asked about their treatment experience in the Device Usability Questionnaire at the end of the treatment period.

Unblinding at the study site will only occur in the case of a SADE (serious adverse event at least possibly related to the device) or UADE (serious and unanticipated/unexpected adverse events at least possibly related to the device) that also requires cessation of device treatment. If this situation seems likely, the Unblinding Investigator, noted in the Delegation of Authority Log, should contact SNS to request approval to unblind. Upon receipt of written permission from the

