Therapeutic CVS has been studied for use in prevention of episodic migraine and in treatment of symptoms of Parkinson's Disease. Results of these studies (including one multisite RCT and one single-site RCT, respectively), resulted in neither serious nor unanticipated/unexpected adverse events related to the study device. Additionally, there was no reduction in balance and no negative change in either mood or cognition.

The following AEs are known, possible side effects of using the investigational device:

More likely:

- Drowsiness
- Dizziness (whirling or spinning sensation; may also be called “giddiness” or vertigo)
- Treatment site discomfort (skin itching, skin irritation felt within the ear canal or around the ear canal or pressure felt within ear canal)

Less likely:

- Nausea
- Vomiting
- Tinnitus
- Headache

All of the potential AEs noted above are expected to resolve soon after use of the investigational device is stopped.

Serious Adverse Device Effect (SADE):

Adverse device effect that has resulted in any of the consequences characteristic of a serious adverse event.

Unanticipated Adverse Device Effect (UADE):

An Unanticipated Adverse Device Effect is a *serious* adverse effect on health or safety or any life-threatening problem or death caused by, or associated with, a device, if that effect, problem, or death was not previously identified in nature, severity, or degree of incidence in the investigational plan or application (including a supplementary plan or application), or any other unanticipated serious problem associated with a device that relates to the rights, safety, or welfare of subjects.

Procedures for AEs

- **Documentation and assessment**

- Following the informed consent process, clinical study participants will be routinely monitored for AEs at study visits and during telephone contacts from the clinical research staff. All AEs, regardless of treatment group, severity or suspected causal relationship to the investigational device, will be recorded on the participants’ source documentation.
- For all AEs, sufficient information will be obtained as to 1) determine the severity of the event (i.e., whether the event should be classified as “*serious*”); 2) assess the causal relationship between the adverse event and the investigational device; and 3) determine the outcome of the event.
- AEs will be followed until the event (or its sequelae) resolves or stabilizes at a level acceptable to the investigator and Device sponsor.

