- If the Sponsor determines that an UADE presents an unreasonable risk to participants, the Sponsor shall terminate all investigations or parts of investigations presenting that risk as soon as possible, no later than 5

working days after the sponsor first received notice of the effect.

Device Deficiencies

A device deficiency is an inadequacy of a medical device related to its identity, quality, durability, reliability, safety, or performance, such as malfunction, misuse or use error and inadequate labeling.

All device deficiencies will be documented, and the device should be returned to the device manufacturer for analysis, if possible. Instructions for returning the investigational device will be provided. Device deficiencies should also be documented in the study participant's source documents in the study binder. Device deficiencies are NOT to be reported as AEs. However, if there is an AE that results from a device deficiency, that specific event would be recorded on the appropriate CRF.

References

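### The assessor is kept off the interim calls, but nothing keeps the assessor out of the adverse-event review at the week-12 and week-17 rating visits

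*Combined protocol and SAP*

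**What the plan says.** Under Randomization, Blinding and Unblinding, the plan separates rating from telephone follow-up: "All assessments will be performed by a study coordinator that does not take part in the interim phone calls". According to the Interim phone calls paragraph, at weeks 3, 6 and 9 "the coordinator will ask about any adverse events, any changes to concomitant medications" and checks for problems with the Device.

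AE collection is not confined to those calls. Under Procedures for AEs, "participants will be routinely monitored for AEs at study visits and during telephone contacts from the clinical research staff". The Schedule of Activities has a row "Review concomitant medications and adverse events", which appears to be marked at the week-12 and week-17 remote and clinic visits. The same AE section says: "All AEs, regardless of treatment group, severity or suspected causal relationship to the investigational device, will be recorded on the participants’ source documentation".

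At the week-12 and week-17 remote visits the study coordinator administers the NMSS, MDS-UPDRS parts II and IV, the modified part III and the MoCA. At week 12 the coordinator also administers the Device usability questionnaire. For the clinic visit a day later, the plan says: "On arrival, the MDS-UPDRS part III and the Timed Up and Go (TUG) will then be administered".

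**The concern.** The evident purpose of keeping the assessor off the calls is to stop the person who rates from hearing about treatment experience. If the same AE question can be put by, or in front of, the assessor at a rating visit, that purpose can be defeated by following the plan as written.

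The information could point to allocation. The AE section lists dizziness among the likelier Device effects. The intervention section says stimulation 2 sends no power to the thermal elements and gives only a minimal vestibular stimulus. An assessor who hears of dizziness at the week-12 remote visit could rate the full MDS-UPDRS part III the next day, and the clinician-rated scales again at week 17, with a view about the arm.

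At stake are the rater-scored change scores. In the Analysis Plan these form part of the clinical side of the correlations used to judge whether the imaging changes explain symptom benefit.

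**Working it through.** The documents give no figure on this point, so the main check sets the sections side by side.

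1. **What the separation covers.** The blinding section takes the assessor off the interim calls only. It says nothing about AE review at visits.
2. **Where AEs are asked about.** The AE section names study visits as well as calls. The last scheduled call is at week 9, so the week-12 visit is the next scheduled contact at which events from the final weeks of treatment can be asked about. In the text copy of the schedule the columns are visibly out of line, so its marks are supporting evidence only. The AE section makes the point without them.
3. **Who is present.** The AE section speaks only of clinical research staff. The only role named at the week-12 and week-17 remote visits is the coordinator giving the ratings. No section names another person for the AE review or sets an order.
4. **Records.** AEs go into participant source documentation, and no section restricts the assessor's access to it.
5. **Other safeguards.** The no-sharing rule covers remarks about warming or cooling, not AE reports. Participants are asked not to discuss their treatment experience in the absence of pain, but a direct AE question invites an answer. The usability questionnaire is an express exception to that request.
6. **A later cue.** At week 17 the ear exam is done only if ear-related AEs remained at the last treatment visit, so performing it is itself informative.

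**Possible size.** No AE rates by arm are given, so the rates below are assumptions. Let pa and ps be the proportions reporting dizziness under stimulation 1 (active) and stimulation 2. With 1:1 allocation:

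- P(active | report) = pa / (pa + ps).
- If the assessor guesses active after a report and stimulation 2 otherwise, the overall proportion correct is 0.5 × pa + 0.5 × (1 − ps).
- With the maximum of 20 participants, 10 per arm, expected reporters = 10 × pa + 10 × ps.

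| Assumed pa v ps | P(active given report) | Overall correct | Expected reporters of 20 |
|---|---|---|---|
| 30% v 5% | 0.30/0.35 = 86% | 0.15 + 0.475 = 62.5% | 3 + 0.5 = 3.5 |
| 30% v 10% | 0.30/0.40 = 75% | 0.15 + 0.45 = 60% | 3 + 1 = 4 |
| 40% v 20% | 0.40/0.60 = 67% | 0.20 + 0.40 = 60% | 4 + 2 = 6 |
| Equal rates | 50% | 50% | depends on the rate |

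The overall gain over chance is (pa − ps)/2, that is, 12.5, 10 and 10 percentage points in the first three rows.

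**The case against.** The strongest reply is that this builds on silence. No section has the assessor eliciting AEs or reading AE records. The visit descriptions list what the coordinator administers, and AE review is not on those lists. A Delegation of Authority Log exists and may divide the tasks. This stands to the extent that a reader might infer that the assessor is unblinded by design, and the documents do not support that.

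A reader might also infer that Device-fault notes reveal side effects, because "Device deficiencies should also be documented in the study participant's source documents in the study binder". They do not support that either. The same section keeps deficiencies apart from AEs and sends any resulting AE to its own form, and nothing shows that faults differ by arm.

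Ear discomfort is a weak cue. It includes pressure in the canal, and headset pressure is the same in both arms, so dizziness is the cue that matters.

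The assumed rates may be too high. The Risk Benefit Assessment reports a low incidence of possibly Device-related AEs in the earlier Parkinson's trial. Listed effects are also expected to resolve soon after use stops, so fresh reports at week 17 should be few. What carries forward to week 17 is mainly what the assessor learned at week 12 or can read in the record.

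Other protections exist: endpoint analysts are blinded, participants are not told that the Device works by temperature, and part III may be videotaped for review. Part III and the Timed Up and Go are done on arrival at the clinic, but that does not help if AEs were discussed with the assessor at the remote visit the day before.

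These replies limit the size of the problem. None of them closes the route.

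**Conclusion.** The point holds as an unclosed route to partial rater unblinding at weeks 12 and 17. It is minor, and no breach is documented. It rests on two readings: that AEs are asked about at the rating visits, which the AE section states, and that nothing in the documents keeps the assessor out of that exchange or its records.

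Its reach is limited to the coordinator- or clinician-rated measures (MDS-UPDRS, NMSS, MoCA, Timed Up and Go) and their exploratory correlations with imaging. A reader might extend it to the main results, but the primary outcomes are pCASL perfusion and cerebrovascular reactivity, which no rater scores. The depression, anxiety, sleepiness and fatigue scales are completed by participants.

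The size is unknown. The 86% to 67% figures should not be read as the degree of unblinding in the trial. They apply only to participants who report, under assumed rates. Across all participants the same assumptions give about 60% to 63% correct guesses, and equal rates give 50%.

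**What to change.** State in the blinding section and the visit descriptions that at weeks 12 and 17 the existing interim-call coordinator does the AE review, and at week 12 also the Device usability questionnaire. Both should follow that visit's ratings and take place without the assessor. The questionnaire needs to be included because it asks directly about treatment experience at a rating visit; moving the AE review alone would leave that route open.

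Keep AE entries, and the reason for any week-17 ear exam, from the assessor until the week-17 ratings are complete. Any spontaneous or urgent report made to the assessor should pass at once to the call coordinator or the investigator, so that safety reporting is not delayed.

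This needs no extra staff and loses no AE information. The cost is one extra hand-over at two visits.

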Any unanticipated problems, serious and unexpected adverse events, deviations or protocol changes will be documented and promptly reported by the principal investigator or designated member of the research team to the IRB and Device sponsor or appropriate government agency if appropriate.

AEs, ADEs, SAEs, SADEs and UADEs will be defined per ISO14155:2011 and/or 21 CFR Part 812, as described below.

Adverse Event (AE):

An AE is any untoward medical occurrence, unintended disease or injury, or untoward clinical signs (including abnormal laboratory findings) in subjects, users or other persons, whether or not related to the investigational medical device. This definition includes events related to the investigational medical device and the procedures involved. For users and other persons, this definition is restricted to events related to the investigational device. AEs will be collected starting from the time the subject signs informed consent until the follow-up period is completed.

Serious Adverse Event (SAE):

A Serious AE (SAE) is an AE that has

- a) Led to death,
- b) Led to serious deterioration in the health of the subject, that either resulted in
 - 1) A life-threatening illness or injury, or
 - 2) A permanent impairment of a body structure or a body function, or
 - 3) In-patient or prolonged hospitalization, or
 - 4) Medical or surgical intervention to prevent life-threatening illness or injury or permanent impairment to a body structure or a body function,
- c) Led to fetal distress, fetal death or a congenital abnormality or birth defect

Adverse Device Effect (ADE):

An Adverse Device Effect (ADE) is an AE related to the use of an investigational medical device.

This definition includes AEs resulting from insufficient or inadequate instructions for use, deployment, implantation, installation, or operation, or any malfunction of the investigational medical device.

This definition includes any event resulting from use error or from intentional misuse of the investigational medical device.

Traditional, diagnostic CVS has been used for roughly a century, and there are no reports in literature of significant adverse events.

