
- **Causality and Severity assessment**
 - The investigator will promptly review documented AEs to determine 1) if there is a reasonable possibility that the adverse event was caused by the investigational device or other study treatments and 2) if the adverse event meets the criteria for “*serious*.”
 - If the investigator’s final determination of causality is “of possible or probable relationship to the investigational device or other study treatments,” the adverse event will be classified as “*associated with the use of the investigational device or other study treatments*” for reporting purposes and escalated to the Device sponsor for further evaluation. If the investigator’s final determination of causality is “*not related* to the investigational device or other study treatments,” this determination and the rationale for the determination will be documented.

- **Investigator Reporting AEs to the Sponsor and responsible IRB Reporting to the Sponsor:**

- Adverse events will be submitted to the Sponsor.
- All serious and/or unanticipated adverse events will be submitted to the sponsor as soon as possible, but in no event later than 10 days after the investigator first learns of the event.
- All serious and/or unanticipated/unexpected adverse events that involves a death must be reported within **24 hours** of discovery.

Reporting to the IRB:

- Investigators are additionally required to submit to their IRB a report of Unanticipated Adverse Device Effect (UADE) as soon as possible, but in no event later than 10 working days after the investigator first learns of the event (21 CFR 812.150(a)(1)). However, if the UADE involves a death, it must be reported within 24 hours of discovery.

UADEs will require unblinding but written permission must first be obtained by the study sponsor.

- **Sponsor Reporting AEs to the FDA or Competent Authority:**

Upon receiving a report of a serious or unanticipated adverse device effect (or unexpected serious adverse device event), the Sponsor will immediately conduct an evaluation of the event/effect and report the results as follows:

- The Sponsor will report the results of an UADE to FDA, reviewing IRB, and participating investigators within 10 working days after the sponsor first receives notice of the effect (21 CFR 812.46[b], 21 CFR 812.150[b][1]). Thereafter, the sponsor shall submit such additional reports concerning the effect, as needed.

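### The adverse event rules use severity to mean serious, specify no intensity scale, and pool the Device with undefined *other study treatments* in one causality class

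*Combined protocol and SAP*

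**What the plan says.** On severity, the Documentation and assessment item under Procedures for AEs states that "sufficient information will be obtained as to 1) determine the severity of the event (i.e., whether the event should be classified as" serious. The next item, Causality and Severity assessment, has the investigator decide on causality and "if the adverse event meets the criteria for" serious. Nothing else in that item concerns severity.

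On causality, the Documentation and assessment item asks staff to "assess the causal relationship between the adverse event and the investigational device". The Causality and Severity assessment item asks instead "if there is a reasonable possibility that the adverse event was caused by the investigational device or other study treatments". A possible or probable answer puts the event into one class covering both sources, which is used for reporting and for escalation to the Device sponsor. The opposite answer, not related, is worded for both sources together as well.

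The definitions are narrower: "An Adverse Device Effect (ADE) is an AE related to the use of an investigational medical device". SADE is built on ADE, and UADE also requires a link to a device.

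The hypercapnia challenge is described under MRI protocol as part of the pCASL imaging. Under Transcranial Doppler (TCD) Sonography, "the participant will receive a second hypercapnia challenge" on the same day. Neither section calls it a treatment.

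**The concern.** Intensity and seriousness are different attributes of an adverse event. Seriousness is a question of outcome, such as death, hospitalization or permanent impairment. Intensity says how bad the event was for the participant. The protocol lists the expected Device effects (drowsiness, dizziness, treatment site discomfort, nausea, vomiting, tinnitus, headache) and reports that the earlier trials produced no serious Device-related event. If that pattern holds, a serious/non-serious field will be constant across the expected effects. It will not distinguish a trivial dizzy spell from one that stopped a session.

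The causality class matters because the sponsor's safety argument, in Risk Benefit Assessment, rests on how often events might be related to Device use. The reporting class defined here does not match that quantity. It may also cover events from something other than the Device, and the protocol does not say what that something is.

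**Working it through.** No power, alpha or sample-size calculation bears on this point. The check is a comparison of sections and one count.

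**1. Severity.** Three uses of the word can be set side by side.
- Documentation and assessment: severity is explained as serious or not.
- Causality and Severity assessment: the only severity question is serious or not.
- UADE definition: a serious effect that was "not previously identified in nature, severity, or degree of incidence in the investigational plan". Here severity is a property over and above being serious, so the protocol uses the word in two senses.

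No mild/moderate/severe scale or equivalent is given in any section.

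**2. Causality.**

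| Section | Relatedness is to |
|---|---|
| Adverse Device Effect (ADE) | Device |
| Procedures for AEs, Documentation and assessment | Device |
| Discontinuation of Study Intervention (individual AE review) | Device |
| Randomization, Blinding and Unblinding (SADE/UADE trigger) | Device |
| Procedures for AEs, Causality and Severity assessment | Device or *other study treatments*, pooled |

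The one section that assigns the reporting class is the one that differs.

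**3. Where a challenge event would go.** The AE definition includes events related to the procedures involved, so an untoward reaction to the hypercapnia challenge is an AE. Two readings are then open.
- The challenge counts as an *other study treatment*. Its events carry the same class as Device effects.
- It does not count. Its events have no causality class, and their link to the challenge is not captured by the scheme.

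The text does not decide between them.

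**4. Exposure.** The inputs are the inclusion criteria (MRI at 3 visits, TCD at 2), the visit descriptions, and Sample size (up to 20 participants).
- Challenges per participant: 3 MRI + 2 TCD = 5.
- Maximum in the trial: 5 × 20 = 100.
- Before any Device session (baseline MRI and TCD): 2. Five weeks after treatment ends (week 17 MRI): 1. Outside the treatment period: 2 + 1 = 3 of 5, or 3 × 20 = 60 of 100.
- At the end-of-treatment clinic visit, up to which participants keep treating: 2 of 5, or 2 × 20 = 40 of 100.

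The Schedule of Activities appears to mark TCD at week 17 too, but that table may be broken in the text available. Taken literally it gives 6 challenges per participant (120 in all), 4 of them outside the treatment period.

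**The case against.** The strongest reply is that a Device-only judgement is already required for every AE, both in Documentation and assessment and in the individual review under Discontinuation of Study Intervention. The pooled class is then only a label that triggers a further look by the sponsor. This stands in part: the Device-only judgement is asked for. But the class used for reporting is a different one, and the protocol does not say which prevails.

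A reader might infer that challenge effects will be counted with Device effects. The documents do not support that. The challenge is described as part of imaging and recording, and treatment in this protocol ordinarily means a Device session. What is established is that the attribution is unclear.

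A reader might also infer that expected effects cannot be graded. Nothing forbids grading, and the AE form is not among the documents, so it may hold an intensity field. The supportable statement is that no scale is specified.

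Nor does it follow that the UADE assessment would lack what it needs. That test applies only to serious effects linked to a device, and such an event would be reported and evaluated individually. The grade of a non-serious dizziness does not enter it.

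Timing gives some protection: onset date would help to separate 3 of the 5 challenges from Device use. It does not separate the 2 at the end-of-treatment visit.

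Finally, this is a mechanistic study of up to 20 people with a device designated non-significant risk, and no stated objective concerns AE intensity. That limits the weight of the point but does not remove it.

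**Conclusion.** The point holds in a limited form. The protocol uses severity to mean serious and states no intensity scale, so the rules as written yield no graded information on the expected non-serious Device effects. Its reporting class for causality does not agree with the Device-only wording used elsewhere, and the attribution of events from up to 100 hypercapnia challenges is left open.

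This rests on the visit descriptions for the count of challenges, and on the protocol text alone for what is recorded, since the AE form has not been seen. How often challenge-related events will occur is not given, so no distortion of an AE rate can be calculated. The perfusion and reactivity comparisons are untouched. The protocol provides for all AEs to be recorded, reviewed and followed, so no failure of participant protection is shown. It is an inexpensive improvement to the safety data and worth making.

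**What to change.** In Procedures for AEs:

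1. Record intensity (mild, moderate, severe) for every AE, in a field separate from serious yes/no, and stop explaining severity as seriousness.
2. Replace the pooled class with two relatedness fields, one for the Device and one for study procedures (hypercapnia challenge, MRI, TCD), together with the onset date. Either define *other study treatments* or remove the term.
3. State that ADE, SADE and UADE are derived from the Device field. The assessment step then agrees with the definitions, the individual AE review and the unblinding rule.

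The cost is two or three more fields on the AE form, slightly more work for site staff, and revised wording in two items of one section.
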